Evaluation of a nonopioid recovery pathway after percutaneous nephrolithotomy will apply the knowledge and experience gained with development of the previous outpatient opioid reduction protocol to percutaneous nephrolithotomy (PCNL), a minimally invasive procedure performed by urologists for nephrolithiasis too large or difficult to treat endoscopically. While previous efforts have targeted outpatient urologic procedures for opioid reduction, procedures like PCNL are opportunities for opioid reduction as well. These procedures with < 24-hour observation often may be the highest yield for intervention as the barrier to receiving opioid pain medication may be lower while they are admitted to the floor. The observation period also prioritizes prompt pain control and timely discharge, which may also lower the threshold for opioid pain medication administration.

Study Design:

We propose a pragmatic pilot study which will prospectively compare a cohort of 15 patients undergoing PCNL prior to implementation of the novel nonopioid pathway to 15 patients undergoing the same procedure utilizing the novel nonopioid pathway. A historical cohort of patients was analyzed to determine the study population size needed to achieve our goals. Sixty-four patients underwent PCNL at The Miriam Hospital in 2018 and approximately 80% of patients were discharged home with a prescription for opioid pain medication (20% opioid-free discharge rate). Current standard of care following PCNL remains the routine prescription of opioid medications for pain control. Since PCNL is a more invasive procedure than ureteroscopy and is a non-natural orifice surgery, we expect to reduce opioid prescriptions from 80% to 50% (50% opioid-free discharge rate). To power a study with a beta of 0.8 and an alpha of 0.05 requires only a small sample size of 13 patients with this large reduction. In order to account for patient drop out and protocol non-adherence, we plan to enroll 30 patients in our pilot study.

The subject population will be adult patients referred to The Miriam Hospital Kidney Stone Center (Lifespan – Providence, RI) and Brown Urology (Brown Physicians, Inc. – Providence, RI) for complex kidney stone disease and scheduled for percutaneous nephrolithotomy (PCNL) during the active study enrollment period who meet inclusion criteria. As the prevalence of nephrolithiasis in the United states is seen more in men (1.4:1 male

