vs female),¹³ we anticipate our patient population to include more men than women. The risk difference between men and women, however, has been narrowing and we would expect that given our anticipated study population size of 30 patients, approximately 12-15 patients will be women. Nephrolithiasis affects all races and given the diverse population of the greater Providence, RI region, we anticipate a significant portion of our study population to be of non-white race. Every effort will be made to offer participation to eligible women and minorities.

Inclusion and Exclusion Criteria:

Patients ≥ 18 years old undergoing primary percutaneous nephrolithotomy at the Miriam Hospital (Lifespan Network, Providence, RI) will be eligible for enrollment. Patients will be excluded if undergoing concurrent non-PCNL procedure, second-look PCNL (subsequent PCNL after primary PCNL), or present with Chronic Kidney Disease Stage ≥ 3 or eGFR < 50 mL/min/1.73m² at time of surgery. Patients with allergy to NSAIDs or have history of NSAID related GI bleeding or ulcers will be excluded.

Inclusion of Women and Minorities:

As the prevalence of nephrolithiasis in the United States is seen more in men (1.4:1 male vs female), we anticipate our patient population to include more men than women. The risk difference between men and women, however, have been narrowing and we would expect that given our anticipated study population size of 25 patients, approximately 10 patients will be women. Nephrolithiasis affects all races and given the diverse population of the greater Providence, RI region, we anticipate a significant portion of our study population to be of non-white race. Every effort will be made to offer participation to eligible women and minorities.

Inclusion of Children

Patients under the age of 18 will not be eligible for participation in the study. The study is aimed at understanding adult nephrolithiasis and the feasibility of nonopioid postoperative pain control after percutaneous nephrolithotomy, and nephrolithiasis of childhood is a distinct clinical entity not addressed by this study.

Vulnerable Subjects:

Special vulnerable populations, such as fetuses, neonates, pregnant women, children, prisoners, or institutionalized individuals will not be eligible for participation in the study.

Recruitment and retention plan:

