Patients referred to The Miriam Hospital Kidney Stone Center / Brown Urology for complex kidney stone disease and scheduled for percutaneous nephrolithotomy (PCNL) during the active study enrollment period who meet inclusion criteria will be offered participation in the study. Our center performs approximately 75 PCNLs yearly and we anticipate enrolling 25 patients, which will be adequate to demonstrate the safety and feasibility of the protocol (see Statistical Design and Power).

Urology housestaff and an attending urologist are on call 24 hours a day. Patients will be encouraged to reach out via telephone for questions concerning the study or continued participation. At the postoperative follow up visit (scheduled for 7-10 days after surgery), the research assistant will administer the Ureteral Stent Symptom Score (USSQ), a validated questionnaire regarding postoperative pain control. This will also function to establish continued participation in the study. Patients will complete their participation in the study 30 days after surgery.

Study Timeline:

Two months after notice of award, eligible patients scheduled for percutaneous nephrolithotomy (PCNL) will be offered participation in the study. The study will accrue patients through for one year or until the enrollment goal (25 patients) has been met. Statistical analysis will be performed following accrual and initial findings will

be summarized and reported per protocol to COBRE Opioids and Overdose as well as ClinicalTrials.gov approximately 24 months after notice of award.

Protocol:

Informed consent will be obtained at the time of consent for surgery in the outpatient urologic clinic setting. Either the principal investigator or the trained research assistant (TBA) will conduct the consenting process. Consent will be in written form. A description of the study will be described by the physician or research assistant and will be provided in written form. Patients deemed able to consent for the surgery will have capacity to consent to participation in the study. Patients not able to consent to surgery will not be eligible for the study. The consent process will inform a volunteer about the study, indicate the participation is voluntary and he/she has the right to stop at any time. Risks will be enumerated in the informed consent form and described verbally during the consent process.

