This is a pragmatic pilot study which will prospectively compare a cohort of 15 patients undergoing PCNL prior to implementation of the novel nonopioid pathway to 15 patients undergoing the same procedure utilizing the novel nonopioid pathway. A historical cohort of patients was analyzed to determine the study population size needed to achieve our goals. Sixty-four patients underwent PCNL at The Miriam Hospital in 2018 and approximately 80% of patients were discharged home with a prescription for opioid pain medication (20% opioid-free discharge rate). Current standard of care following PCNL remains the routine prescription of opioid medications for pain control. Since PCNL is a more invasive procedure than ureteroscopy and is a non-natural orifice surgery, we expect to reduce opioid prescriptions from 80% to 50% (50% opioid-free discharge rate). To power a study with a beta of 0.8 and an alpha of 0.05 requires only a small sample size of 13 patients with this large reduction. In order to account for patient drop out and protocol non-adherence, we plan to enroll 30 patients in our pilot study.

The subject population will be adult patients referred to The Miriam Hospital Kidney Stone Center (Lifespan – Providence, RI) and Brown Urology (Brown Physicians, Inc. – Providence, RI) for complex kidney stone disease and scheduled for percutaneous nephrolithotomy (PCNL) during the active study enrollment period who meet inclusion criteria. As the prevalence of nephrolithiasis in the United States is seen more in men (1.4:1 male vs female),¹³ we anticipate our patient population to include more men than women. The risk difference between men and women, however, has been narrowing and we would expect that given our anticipated study population size of 30 patients, approximately 12-15 patients will be women. Nephrolithiasis affects all races and given the diverse population of the greater Providence, RI region, we anticipate a significant portion of our study population to be of non-white race. Every effort will be made to offer participation to eligible women and minorities.

The protocol will be assessed for feasibility of implementation and safety through analysis of acceptability (number of enrolled patients / patients approached), adherence to and acceptability of the protocol (dropout of

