enrolled patients and patient satisfaction via a validated questionnaire (USSQ) and adverse events (AEs) while inpatient and following discharge. Statistical analysis of the pre- and post- intervention groups will be performed to assess for significant overall reduction in opioid prescriptions. Analysis of the patient characteristics and primary / secondary outcomes of the patients will be used to assess potential reasons for opioid necessity following PCNL.

Data Safety Plan:

A minimum of PHI (protected health information) that might identify patient participation will be collected for data analysis purposes. HIPAA identifiers that will be collected include medical record number (MRN) and date of surgery. All HIPAA identifiers will be coded and a de-identified separate database will be held electronically in a secure password protected workstation.

Potential Risks:

Besides the risks of the surgical procedure itself which apply to participants and nonparticipants equally, potential risks of the study include inadequate treatment of pain postoperatively. Patients will be queried prior to discharge on their comfort level regarding discharge without opioid pain medications, and opioids will not be withheld if requested or if the physician feels the patient will not be successfully discharged without opioid prescription. If pain is not controlled after discharge, urology housestaff and an attending urologist are available 24 hours a day for telephone consultation and pain medication refill requests.

This risk is not unique to study participants. Following surgery, there is always a risk of inadequate treatment of pain postoperatively, even with those prescribed opioids. The benefits of avoiding opioids have been well described and potentially outweigh the risks of undertreatment of pain. Additionally, patients exposed to opioids are at risk for opioid induced hyperalgesia. Opioid exposure has been linked to chronic opioid use in patients undergoing ureteroscopy as well, and opioid avoidance can mitigate that risk. Other potential risks including the risks to privacy and/or confidentiality due to data breach will be mitigated with the data safety plan above.

Informed Consent and Assent:

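### Thirteen patients do not give 80% power for 80% vs 50%: the planned two-cohort comparison needs about 39 per cohort, and 15 vs 15 has 25–42% power two-sided

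*Combined protocol and SAP*

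**What the plan says.** Study Design and the Statistical Analysis Plan carry the same text. The study will "prospectively compare a cohort of 15 patients undergoing PCNL prior to implementation of the novel nonopioid pathway to 15 patients undergoing the same procedure" under the pathway. The 2018 series of 64 patients gives a prescription rate of about 80%, and the pathway is expected to bring it to 50%. From this the plan concludes: "To power a study with a beta of 0.8 and an alpha of 0.05 requires only a small sample size of 13 patients". It then adds: "In order to account for patient drop out and protocol non-adherence, we plan to enroll 30 patients in our pilot study". It does not name the test, its sidedness or the formula, and does not say whether 13 is per cohort or in total.

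Discharge without an opioid prescription is one of four items listed under the primary study outcome. Data Analysis and the Statistical Analysis Plan both state: "Statistical analysis of the pre- and post- intervention groups will be performed to assess for significant overall reduction in opioid prescriptions".

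The enrolment target differs between sections. Study Design and the Statistical Analysis Plan use 30. The recruitment and retention plan says "we anticipate enrolling 25 patients, which will be adequate to demonstrate the safety and feasibility of the protocol", Study Timeline repeats 25 as the enrolment goal, and the section on inclusion of women and minorities says "given our anticipated study population size of 25 patients, approximately 10 patients will be women".

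**The concern.** A 30-point difference between two proportions in this range normally needs several dozen patients per group, so 13 is implausible on sight. The wording adds doubt: beta is the type II error rate, so a beta of 0.8 read literally means 20% power.

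Opioid-free discharge is the only primary outcome with a stated power, and it is to be tested for significance. The plan has no rule for reading a non-significant result. A reader who trusts the power statement would take such a result as evidence against the pathway, although the study would be more likely than not to produce it in a two-sided test even if the pathway worked as expected. The study is meant to inform a later randomised trial, so the misreading could carry forward.

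**Working it through.** **Inputs (Study Design and Statistical Analysis Plan).** p1 = 0.80, p2 = 0.50, difference d = 0.30, alpha = 0.05, 15 vs 15. Power is read as 0.80. Sidedness is not stated, so both are shown. Normal quantiles: 1.9600 (two-sided), 1.6449 (one-sided), 0.8416 (80% power).

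**1. Can 13 be reproduced for two cohorts?** Pooled formula, with mean proportion 0.65:

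n per cohort = [z_α·√(2·0.65·0.35) + z_β·√(0.80·0.20 + 0.50·0.50)]² / d²

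- Two-sided: (1.9600·0.6745 + 0.8416·0.6403)² / 0.09 = (1.3221 + 0.5389)² / 0.09 = 38.5, so 39.
- One-sided: (1.6449·0.6745 + 0.5389)² / 0.09 = (1.1095 + 0.5389)² / 0.09 = 30.2, so 31.

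| Method, n per cohort | Two-sided | One-sided |
|---|---|---|
| Unpooled, (z_α + z_β)²·0.41 / 0.09 | 36 | 29 |
| Arcsine | 38 | 30 |
| Pooled | 39 | 31 |
| Fisher's exact, by enumeration | 44 | 36 |
| Pooled with continuity correction | 45 | 37 |

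None gives 13, per cohort or in total.

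**2. Where 13 might come from.** The documents do not say. Two routes arrive at it:

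- A one-sample, one-sided test of the pathway cohort against a fixed 80%: (1.6449·√0.16 + 0.8416·√0.25)² / 0.09 = (0.6579 + 0.4208)² / 0.09 = 12.93. Even in that design, the exact binomial test at n = 13 (reject at 6 or more opioid-free, actual alpha 0.030) has 70.9% power.
- A two-sided, continuity-corrected two-sample formula at 20% power, taking beta literally: 12.60 per cohort.

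Neither is 80% power for the planned comparison.

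**3. Power at the planned sizes.** For every pair of counts (x, y), the binomial probabilities under 80% and 50% are multiplied, then summed over the pairs with p ≤ 0.05.

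| Pre vs pathway | Two-sided, Fisher / chi-square | One-sided, Fisher / chi-square |
|---|---|---|
| 15 vs 15 | 24.6% / 41.9% | 37.3% / 55.6% |
| 13 vs 13 (two lost per cohort) | 25.6% / 40.9% | 35.4% / 49.5% |
| 12 vs 13 (25 in total, split assumed) | 28.3% / 33.3% | 32.6% / 47.7% |
| 6 vs 7 (13 in total) | 9% / 22% | 16% / 31% |

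Chi-square is uncorrected. Boschloo's test at 15 vs 15 lies between the two: 37.3% two-sided, 52.0% one-sided. Two-sided Fisher power does not fall steadily as n shrinks, because its actual size jumps with the discrete counts; that is why it is slightly higher at 13 vs 13 than at 15 vs 15.

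Check at larger n, two-sided: 39 vs 39 gives 81.3% with chi-square; 44 vs 44 gives 80.2% with Fisher.

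**4. What 15 vs 15 can detect.** Two-sided power of 80% needs a fall from 80% to about 30% (chi-square) or 24% (Fisher).

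**5. An attainable result.** With 12/15 vs 7/15 prescribed opioids, the drop is 5/15 = 33 points, more than assumed. Two-sided p is 0.058 (chi-square) or 0.128 (Fisher), and the Newcombe 95% interval for the reduction runs from −1 to +59 points. With 12/15 vs 6/15, a 40-point drop, p is 0.025 or 0.060.

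**The case against.** The strongest reply is that this is a pilot. Its stated purpose is feasibility data for a randomised trial, the third aim is only to begin reducing prescribing, and the recruitment section calls its number adequate for safety and feasibility, not for an efficacy test. Three of the four primary outcomes need no power calculation. All of this stands, and it is why no larger sample is asked for. It does not excuse the sentence: the plan chose to claim power for a primary outcome and to test it for significance.

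A second reply is that 13 came from comparing the pathway cohort with the 2018 rate. That is plausible, since the historical series is cited just before, but the plan enrols 15 pre-pathway patients as the comparator and their sampling error has to be counted. Even against all 64 historical patients, 13 new patients give only about 61% power two-sided or 71% one-sided by normal approximation; 26 or 19 would be needed.

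A third point is that the ranges depend on a test the plan does not name. That is true, but no choice comes near 80%. The most favourable figure, 56%, comes from a one-sided uncorrected chi-square test whose actual type I error at 15 vs 15 is 5.8% when both rates are 80%, so it is somewhat flattering. The two-sided chi-square test has a size of about 5.0% there, so the main two-sided range is unaffected.

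**Conclusion.** The concern holds. Thirteen patients do not give 80% power for the comparison the plan describes. About 39 per cohort are needed two-sided (36–45 across methods) or 31 one-sided (29–37). The 15 vs 15 design has 25–42% power two-sided or 37–56% one-sided, so the implied 80% is about two to three times too high for a two-sided test (80/42 = 1.9; 80/25 = 3.2).

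This rests on the plan's own rates of 80% and 50%, alpha 0.05, power read as 80%, and independent cohorts with all 30 patients evaluable. If 25 is the true target, split 12 and 13, two-sided power is 28–33%. How 13 was derived remains unknown, and the conclusion does not depend on it. The defect lies in the power statement and in how the significance test will be read, not in the feasibility aims.

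**What to change.** In Study Design and the Statistical Analysis Plan:

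1. Delete the statement that 13 patients suffice.
2. Replace the beta of 0.8 with the intended wording, presumably power of 80% (beta 0.2).
3. Name the test and its sidedness.
4. Reconcile the target of 30 with the 25 in the sections on inclusion of women and minorities, recruitment and retention, and Study Timeline, together with the dependent count of about 10 women.
5. State power at the reconciled size, keeping only the figures for the chosen test. If 30 and a two-sided test stand, for example:

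> With 15 patients per cohort and two-sided alpha 0.05, power to detect 80% vs 50% is about 42% (chi-square) or 25% (Fisher's exact). Power of 80% is reached only for a fall to about 30% (chi-square) or 24% (Fisher's exact). About 39 (chi-square) or 44 (Fisher's exact) patients per cohort would be needed for 80% vs 50%.

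6. Report the risk difference with its 95% confidence interval beside the test, and state that a non-significant result will not be read as showing no reduction. This last step does not correct the arithmetic, but it supplies the reading rule that the plan lacks.

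The cost is a wording change in two sections and one enrolment figure made consistent in three others. No patients, visits or procedures are added. The stated power becomes less favourable.
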